### **New Lesions**

The appearance of new malignant lesions indicates PD. New lesion should be unequivocal (eg, not attributable to differences in imaging technique, or change in imaging modality or findings not attributable to tumor). If a new lesion is equivocal, for example due to its small size, continued therapy and follow-up assessment will clarify the etiology of the disease. If repeat scans confirm there is definitely a new lesion, then progression should be declared using the date of the initial scan.

The use of FDG-PET is sometimes reasonable to complement a CT scan assessment of a PD (particularly for possible ‘new’ disease). New lesions on the basis of FDG-PET imaging can be identified according to the following algorithm:

Negative FDG-PET at baseline, with a positive FDG-PET at follow-up;

No FDG-PET at baseline and a positive FDG-PET at follow-up: if the positive FDG-PET at follow-up corresponds to a new site of disease confirmed by CT, this is PD.

If the positive FDG-PET at follow-up is not confirmed as a new site of disease on CT, additional follow-up CT scans are needed to determine if there is truly progression occurring at that site (if so, the date of PD will be the date of the initial abnormal FDG-PET scan).

If the positive FDG-PET at follow-up corresponds to a pre-existing site of disease on CT that is not progressing on the basis of the anatomic images, this is not PD.

### **Confirmation of Tumor Response**

Confirmation of response is required for non-randomized trials with primary endpoint of response, but is not required in randomized studies since the control arm serves as appropriate means of interpretation of data.

### **Determination of Overall Response by the RECIST 1.1 Criteria**

When both target and non-target lesions are present, individual assessments will be recorded separately. The overall assessment of response will involve all parameters as depicted in Table 1.

**Table 1. Response Evaluation Criteria in Solid Tumors**

Target lesions	Non-target lesions	New Lesions	Overall response
CR	CR	No	CR
CR	Non-CR/non-PD	No	PR
CR	Not evaluated	No	PR
PR	Non-PD or not all evaluated	No	PR
SD	Non-PD or not all evaluated	No	SD
Not all Evaluated	Non-PD	No	NE
PD	Any	Yes or No	PD
Any	PD	Yes or No	PD
Any	Any	Yes	PD
CR = complete response, PR = partial response, SD = stable disease,			
PD = progressive disease, and NE = inevaluable.			

### **Best overall response**

The best overall response is determined once all the data for the patient is known. Best response in trials in which confirmation of complete or partial response is not required (ie, randomized trials) is defined as the best response across all time points (for example, a patient who has SD at first assessment, PR at second assessment, and PD on last assessment has a best overall response of PR). When SD is believed to be the best response, it must also meet the protocol specified minimum time from baseline. If the minimum time is not met when SD is otherwise the best time point response, the patient's best response depends on the subsequent assessments. For example, a patient who has SD at first assessment, PD at second and does not meet minimum duration for SD, will have a best response of PD. The same patient lost to follow-up after the first SD assessment would be considered inevaluable.

When confirmation of CR and PR is required (ie, non-randomized trials with primary endpoint of response), the best overall response is defined according to the tumor response along the study. Complete or partial responses may be claimed only if the criteria for each are met at a following time point as specified in the protocol (generally 4 weeks later). In this circumstance, the best overall response can be interpreted as in Table 2.

**Table 2. Best overall response when confirmation of CR and PR required**

Overall response First time point	Overall response Subsequent time point	BEST overall response
CR	CR	CR
CR	PR	SD, PD or PR a
CR	SD	SD provided minimum criteria for SD duration met, otherwise, PD
CR	PD	SD provided minimum criteria for SD duration met, otherwise, PD
CR	NE	SD provided minimum criteria for SD duration met, otherwise NE
PR	CR	PR
PR	PR	PR

PR	SD	SD
PR	PD	SD provided minimum criteria for SD duration met, otherwise, PD
PR	NE	SD provided minimum criteria for SD duration met, otherwise NE
NE	NE	NE
CR = complete response, PR = partial response, SD = stable disease, PD = progressive disease, and NE = inevaluable.		
a If a CR is truly met at first time point, then any disease seen at a subsequent time point, even disease meeting PR criteria relative to baseline, makes the disease PD at that point (since disease must have reappeared after CR). Best response would depend on whether minimum duration for SD was met. However, sometimes 'CR' may be claimed when subsequent scans suggest small lesions were likely still present and in fact the patient had PR, not CR at the first time point. Under these circumstances, the original CR should be changed to PR and the best response is PR.		

Patients with a global deterioration of health status requiring discontinuation of treatment without objective evidence of disease progression at that time should be reported as 'symptomatic deterioration'. Every effort should be made to document objective progression even after discontinuation of treatment. Symptomatic deterioration is not a descriptor of an objective response: it is a reason for stopping study therapy. The objective response status of such patients is to be determined by evaluation of target and non-target lesions.

In some circumstances it may be difficult to distinguish residual disease from normal tissue. When the evaluation of CR depends upon this determination, it is recommended that the residual lesion be investigated (fine needle aspirate/biopsy) before assigning a status of complete response. FDG-PET may be used to upgrade a response to a CR in a manner similar to a biopsy in cases where a residual radiographic abnormality is thought to represent fibrosis or scarring. The use of FDG-PET in this circumstance should be prospectively described in the protocol and supported by disease specific medical literature for the indication. However, it must be acknowledged that both approaches may lead to false positive CR due to limitations of FDG-PET and biopsy resolution/ sensitivity.

6.4. Sub-Group Analyses.....	14
7. REPORTING CONVENTIONS.....	14
8. ATTACHMENTS.....	14
8.1. Attachment 1: Dummy table	14

Statistical Analysis Plan for rPMS

1. Rationale and Background

Renal cell carcinoma (RCC) accounts for 85% of kidney cancers, and is a collection of different types of tumors that arise from the renal epithelium. Renal cell carcinoma (RCC) is diagnosed in approximately 170,000 patients worldwide annually, resulting in 82,000 deaths.

Early stage disease does not typically produce significant clinical signs or symptoms, consequently 25-30% of newly diagnosed patients present with advanced (including locally invasive or advanced) or unresectable disease. The 5-year survival rate for advanced RCC is estimated to be $\leq 10\%$.

Most RCCs are highly vascularised tumors that over-express a number of growth factors, including VEGF (Vascular endothelial growth factor), PDGF (Platelet-derived growth factor) and fibroblast growth factor (FGF). The clear cell RCC subtype represents approximately 85% of the RCC population and frequently displays allelic loss on chromosome 3p, accompanied by mutational inactivation of the von Hippel-Lindau (VHL) tumor suppressor gene. VHL-associated RCC are known for their vascularity and these tumors produce high levels of vascular endothelial growth factor (VEGF). In addition, recent studies suggest that in sporadic clear cell RCC, increased expression of VEGF is closely correlated with neovascularization, which is a prerequisite of tumor growth and metastasis.

INLYTA[®], a substituted indazole derivative, is an oral, potent, and selective inhibitor that blocks signal transmission via vascular endothelial growth factor receptor (VEGFR-1, -2 and -3) which is related to vascularization of tumors and tumor proliferation.

INLYTA[®] was first approved as new medicine on 22 Aug 2012. As required for any new medication approved by Ministry of Food and Drug Safety (MFDS), safety and efficacy information of new medication should be provided at minimum 3,000 subjects administered in the setting of routine practice during the initial 6 years after the approval. However, based on MFDS's review upon Pfizer Korea's request, additional 3 years of study period has been granted to collect safety and efficacy information of minimum of 100 subjects.

2. Study Objective(s) and Others

2.1. Objectives

The objective of this study is to monitor usage of INLYTA[®] in real practice including adverse events on INLYTA[®].

2.2. Study Design

Observational, non-interventional drug and multi-center study in which subjects will be administered as

Statistical Analysis Plan for rPMS

part of routine practice at Korean health care centers by accredited physicians. At least 3,000 subjects should be enrolled in this study based on the Article 6 of "Basic Standards for the Re-examination of New Medicines" notified by MFDS. However, with additional 3 years of study period, at least 100 subjects who are being treated with INLYTA® within the approved indication will be studied for total of 9 years according to the review result by the MFDS per Pfizer's request to adjust the number of subjects. The study can be performed in Korean health care centers where INLYTA® is prescribed for advanced renal cell carcinoma (aRCC) after failure of one prior systemic therapy which is the indication for INLYTA® and where post-marketing study is allowed by institutions.

To achieve the target sample size, the study is being conducted in prospective study design and retrospective study design.

Patients to whom INLYTA® is first administered or patients who are already on INLYTA® during the study period should be enrolled in the study. Observation should be done from treatment initiation of INLYTA® for at least 28 calendar days. There are no visits or activities mandated by this study and routine observation will be done during INLYTA® treatment.

2.3. Study Population

All subjects enrolled should meet the usual prescribing criteria for INLYTA® as per the Local Product Document (LPD) and should be entered into the study at the physician's discretion.

2.3.1. Inclusion Criteria

Subjects must meet all of the following inclusion criteria to be eligible for inclusion in the study:

1. Patients diagnosed as advanced renal cell carcinoma (aRCC) after failure of one prior systemic therapy.
2. Patients to whom INLYTA® is first administered or patients who are already on INLYTA® during the study period
3. Evidence of a personally signed and dated informed consent document indicating that the patient (or a legally acceptable representative) has been informed of all pertinent aspects of the study.

2.3.2. Exclusion Criteria

Subjects meeting any of the following criteria will not be included in the study:

1. Any patient who does not agree that Pfizer and companies working with Pfizer use his/her information
2. Patients with hypersensitivity to axitinib or to any other component of INLYTA®
3. Patients under 18
4. Pregnant women

Statistical Analysis Plan for rPMS

2.4. Sample size Considerations

Per MFDS regulation, at least 3,000 subjects were required for the study initially. However, based on the decision from MFDS on April 26, 2018, at least 100 subjects who are eligible according to '2.3 Study Population' will be observed for total of 9 years.

3. Analysis Populations

3.1. Safety Analysis Set

Safety analysis set will be included all subjects who have been administered INLYTA® at least once and evaluated with safety-related endpoints at least once.

The case below shall be excluded from the safety analysis set in the following order:

- 1) Subjects who have been already completed for INLYTA® prior to the contract date.
- 2) Subjects who have not been administered INLYTA®.
- 3) Subjects who have not met the inclusion/exclusion criterion.
- 4) Subjects who have not been evaluated for any safety-related endpoints.
- 5) Subjects who have any significant protocol violation.

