#### **3.2.1. Inclusion criteria**

Subjects must meet all of the following inclusion criteria to be eligible for inclusion in the study:

1. Patients diagnosed as advanced renal cell carcinoma (aRCC) after failure of one prior systemic therapy.
2. Patients to whom INLYTA® is first administered or patients who are already on INLYTA® during the study period
3. Evidence of a personally signed and dated informed consent document indicating that the patient (or a legally acceptable representative) has been informed of all pertinent aspects of the study.

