### 3.5.4.9. Safety

#### 3.5.4.9.1. Adverse Event

Every observed and reported adverse event, regardless of the causal relationship with the study drug, must be recorded on an adverse event section in case report forms. The query pattern of experience of adverse event to the subjects is as follow;

Patients who are prescribed with INLYTA® for the first time during the study period: “Have you had any health problem since last visit?”

Patients who are already on INLYTA® at the time of enrollment: all safety information will be collected from medical chart since the date of treatment initiation.

For adverse events repeating before and after administrating the study drug, record the date adverse event was first experienced and the date adverse event resolved. Background information on INLYTA® can be obtained from the current version of the local product document, which is the single reference safety document (SRSD) for information relating to INLYTA®.

Check either ‘yes’ or ‘no’ in adverse event section. If ‘yes’, record in detail.

- Adverse events: Record the name of adverse event. If possible, specify diagnosis, not individual symptoms. Record the name according to National Cancer Institute Common Terminology Criteria for Adverse Events (CTCAE) Version 5.0.
- Date of onset: Record the date of onset. Record approximate date if an actual date is unknown.
- Date of resolution: Record the date of resolution. Record approximate date if an actual date is unknown.
- Severity: Severity evaluation of adverse event must be done according to the NCI CTC grade.
  - The physician will use the following definitions of severity in accordance with the National Cancer Institute Common Terminology Criteria for Adverse Events (CTCAE) Version 5.0 to describe the maximum intensity of the adverse event:

Grade	Definition
Grade 1	Mild; asymptomatic or mild symptoms; clinical or diagnostic observations only; intervention not indicated.
Grade 2	Moderate; minimal, local or noninvasive intervention indicated; limiting age-appropriate instrumental ADL*.
Grade 3	Severe or medically significant but not immediately life-threatening; hospitalization or prolongation of hospitalization indicated; disabling; limiting self care ADL**.
Grade 4	Life-threatening consequences; urgent intervention indicated.
Grade 5	Death related to AE.

Activities of Daily Living (ADL)

\*Instrumental ADL refer to preparing meals, shopping for groceries or clothes, using the telephone, managing money, etc.

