3.2. Efficacy Analysis Set

Efficacy analysis set will be included subjects to whom INLYTA® is administered INLYTA® at least once. Subjects who are excluded from the safety analysis set shall be excluded from the efficacy analysis set.

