3.4. Sub-Group Analysis Set

Sub-group analysis will be conducted for safety analysis set and efficacy analysis set for:

- Sub-group 1: Subjects who are first administered INLYTA® during the study period
- Sub-group 2: Subjects who has continued administration of INLYTA® since the time prior to the contract date

Statistical Analysis Plan for rPMS

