4.2. Efficacy Endpoints

- Tumor response based on RECIST 1.1
- Objective Response Rate (ORR)

ORR will be defined as the number of subjects who achieve a best overall response of complete response (CR) or partial response (PR), divided by the total number of subjects in efficacy analysis set.

- Progression-free survival (PFS)

PFS is defined as the time from first dose of study medication to first documentation of objective tumor progression, or to death due to any cause, whichever occurs first.

- Time to progression (TTP)

TTP is defined as the time from the first dose of study medication to objective tumor progression excluding death.

5. General Consideration

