6.2. Safety Analyses

Safety analyses will be performed based on data of safety analysis set. All adverse events in CRF will be classified by System Organ Class (SOC) and Preferred Term (PT) according to the latest version of Medical Dictionary for Regulatory Activities (MedDRA).

- 1) All adverse events investigated after administration of INLYTA® will be summarized with the number of subjects having adverse events, incidence of adverse events with 95% confidence interval (CI) and the number of adverse events by categorizing as follows.
 - Serious adverse events and serious adverse drug reactions
 - Unexpected serious adverse events and unexpected serious adverse drug reactions
 - Unexpected adverse events and unexpected adverse drug reactions
 - Adverse events and adverse drug reactions
- 2) All adverse events investigated after administration of INLYTA® will be summarized with the frequency and percentage of adverse events by categorizing as follows.

Statistical Analysis Plan for rPMS

- Occurrence status of adverse events by their severity
 - Grade 1 (Mild)
 - Grade 2 (Moderate)
 - Grade 3 (Severe or medically significant)
 - Grade 4 (Life-threatening consequences)
 - Grade 5 (Death related to AE)
- Occurrence status of adverse events by their outcome
 - Recovered
 - Recovered with sequelae
 - Recovering
 - Not recovered
 - Unknown
- Occurrence status of adverse events by their seriousness
 - SAE
 - Results in death
 - Is life-threatening
 - Requires inpatient hospitalization or prolongation of hospitalization
 - Results in persistent or significant disability/incapacity (substantial disruption of the ability to conduct normal life functions)
 - Results in congenital anomaly/birth defect
 - Other important medical event: if it is determined that the event may jeopardize the subject or may require intervention to prevent one of the other outcomes listed in the definition above
 - Non-SAE
- Occurrence status of adverse events by their causality to INLYTA®
 - Related to INLYTA®: ① Certain
 - ② Probable/likely
 - ③ Possible
 - ⑤ Conditional/unclassified
 - ⑥ Unaccessible/unclassifiable
 - ⑦ Not applicable
 - Not related to INLYTA®: ④ Unlikely
- Occurrence status of adverse events by their other causality (In case of 'not related to INLYTA®')
 - Disease under the study
 - Other diseases
 - Concomitant treatment drug or non-drug

Statistical Analysis Plan for rPMS

- Others
- Occurrence status of adverse events by action

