6.4. Sub-Group Analyses

The following analyses will be performed for subjects who are prescribed with INLYTA® for the first time and for subjects who are already on INLYTA®, separately.

- 1) [6.2. Safety Analyses] - 1) ~ 4)
- 2) [6.3. Efficacy Analyses] - 1) ~ 5)

7. Reporting Conventions

Continuous variables will be summarized by descriptive statistics including n, mean, SD, SE, median, minimum and maximum, and categorical variables will be presented in frequency and percentage. Summary statistics including mean, SD, SE, median, minimum and maximum, etc. will be reported to two decimal places using rounding off.

The p-values through the statistical test will be reported to four decimal place and if p-values smaller than 0.0001 will be written as '<0.0001'.

8. Attachments

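### Total ORR and AE results pool new users with pre-contract starters still on INLYTA at the contract date, with no sub-group adjustment and no estimate named as the main one

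*SAP*

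**What the plan says.** Protocol 3.2.1 admits "Patients to whom INLYTA® is first administered or patients who are already on INLYTA® during the study period". SAP 3.1 then removes, as the first of five ordered exclusions, "Subjects who have been already completed for INLYTA® prior to the contract date". SAP 3.2 adds: "Subjects who are excluded from the safety analysis set shall be excluded from the efficacy analysis set". What remains of the pre-contract starters is defined in SAP 3.4 as "Sub-group 2: Subjects who has continued administration of INLYTA® since the time prior to the contract date".

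SAP 6.2 states: "Safety analyses will be performed based on data of safety analysis set". ORR in SAP 4.2 is the number of CR or PR best responses "divided by the total number of subjects in efficacy analysis set". Tables 8 and 26 have columns for Sub-group 1, Sub-group 2 and Total. The main versions of Tables 23-25 (AEs) and 29-31 (ORR) use the whole set, with chi-square or Fisher tests and logistic regression. No sub-group stratum or covariate is specified.

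SAP 6.4 repeats safety items 1-4 and efficacy items 1-5 "for subjects who are prescribed with INLYTA® for the first time and for subjects who are already on INLYTA®, separately". SAP 3.5 and Table 37 describe AEs of treated subjects who were excluded. Protocol 3.5.4.1 and 3.9.2 ask for new users, patients already on drug, and all enrolled patients. Neither document says which of the three is the main estimate.

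**The concern.** A patient who started before the site contract and soon stopped, for toxicity or primary progression, cannot appear in either analysis set. A patient who started at the same time and did well can. Sub-group 2 is therefore a survivor sample. Its best responses, and on one reading its AEs, are nevertheless counted from first dose and added to those of new users.

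The AE monitoring objective and the ORR endpoint are read from proportions of subjects. If the Total column is taken as the study's result, ORR reflects selection as well as drug effect, and early treatment-ending toxicity is thinned out. Ascertainment differs too. New users are asked about health problems since the last visit, whereas for patients already on drug "all safety information will be collected from medical chart since the date of treatment initiation". In the pooled factor analyses, any characteristic that differs between the sub-groups can look associated with AEs or response for these reasons alone. Duration of administration, a factor in Tables 24 and 30, will tend to differ by construction.

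**Working it through.** There is no planned figure to reproduce. The sample of at least 100 was set by the regulator, and the documents give no expected ORR, AE rate, time on drug or split between sub-groups. All rates below are assumptions. Write f for the Sub-group 2 share of the analysis set.

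**1. Direction for ORR.** Assume steady starts and a snapshot at the contract date. Let p be the true ORR and k the ratio of mean time on drug, responders to non-responders. Then

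Sub-group 2 ORR: q = pk / (pk + 1 − p); pooled ORR = (1 − f)p + fq.

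With p = 20%: k = 1 gives q = 20% (no bias); k = 2 gives 0.40/1.20 = 33.3%; k = 3 gives 0.60/1.40 = 42.9%. At f = 0.5 the pool is 26.7% (k = 2) or 31.4% (k = 3). The sign depends only on k > 1.

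**2. Size for ORR with a bounded look-back.** Assume 20% responders, 50% stable and 30% primary progressors, with exponential time on drug and medians of 14, 8 and 2.5 months (means μ = median/ln 2 = 20.2, 11.5 and 3.6). First dose is uniform over the L months before contract. The chance of still being on drug at contract is S = (μ/L)(1 − e^(−L/μ)).

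| L (months) | S: responder / stable / progressor | Sub-group 2 ORR | Pool f = 0.25 | f = 0.5 | f = 0.75 |
|---|---|---|---|---|---|
| 6 | 0.865 / 0.780 / 0.487 | 0.173/0.709 = 24.4% | 21.1% | 22.2% | 23.3% |
| 12 | 0.754 / 0.622 / 0.290 | 0.151/0.549 = 27.5% | 21.9% | 23.7% | 25.6% |
| 24 | 0.585 / 0.421 / 0.150 | 0.117/0.372 = 31.4% | 22.9% | 25.7% | 28.6% |

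A true 20% therefore becomes about 21% to 29%. At f = 0.10 it is only 20.4% to 21.1%.

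**3. Early treatment-ending toxicity.** Assume 15% stop for an AE (median 2 months on drug) and the rest have a median of 8 months. For L = 6, the share in Sub-group 2 is 0.15 × 0.421 / (0.15 × 0.421 + 0.85 × 0.780) = 8.7%. For L = 12 and 24 it is 6.3% and 4.8%. A 50:50 pool shows about 12%, 11% and 10%. These are subject-level shares and match no planned table: Table 22 counts events by action, and its discontinuation category in SAP 6.2 merges permanent and temporary stops with delays.

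**4. Crude any-AE incidence.** Protocol 3.5.4.9.1 collects AEs of patients already on drug back to first dose. Protocol 5.1.2 starts their safety reporting period at informed consent. A simulation of 2,000,000 subjects assumed 10% early AE stoppers (mean 1.5 months on drug), a mean of 9 months for the rest, a first-other-AE hazard of 0.1 per month, 3 months of follow-up and starts spread over 36 months before contract:

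| Start of AE collection for patients already on drug | New users | Sub-group 2 | Pool at f = 0.5 |
|---|---|---|---|
| First dose | 29.0% | 58.8% | (29.0 + 58.8)/2 = 43.9% |
| Consent (taken as the contract date) | 29.0% | 23.5% | (29.0 + 23.5)/2 = 26.3% |

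The sign reverses with the reading, so no direction can be claimed.

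**5. Overlap of the sub-groups.** Sub-group 1 is defined by a first dose within the study period, which under Protocol 3.5.1 runs from approval on 22 Aug 2012. A patient who started after that date but before the site's contract, and continued, meets both definitions. Protocol 3.5.4 ties first-time patients to the executed contract; SAP 3.4 does not.

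**The case against.** Much of the case on the other side stands.

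- The new-user results already exist in the plan. SAP 6.4 and the programming notes repeat the relevant tables by sub-group, and Tables 8 and 26 show the columns side by side. A reader might infer that nothing is split by sub-group; that is wrong. What is missing is any adjustment within the pooled analyses and a statement of which column is the estimate.
- Excluded treated subjects are not lost for safety, since SAP 3.5 and Table 37 report their AEs. Their responses never return to ORR.
- A reader might infer that total any-AE incidence is understated. The documents do not support this: longer exposure with look-back to first dose can raise it, and Tables 8-15 do not isolate early AEs.
- A reader might blame SAP 3.1 item 1 alone. The protocol itself enrols and takes consent from patients already on drug, so deleting the item would not remove the selection.
- The ORR direction is likely rather than certain. Subjects who are not evaluable or not assessed stay in the denominator, and Protocol 3.5.4 asks for data on patients already on drug only as far as possible. Missing scans in Sub-group 2 would pull its ORR down, and the calculation omits this.
- The retrospective part exists to reach the target sample size, so the new-user group may be small. The exact 95% interval is 12.7% to 29.2% for 20/100 and 6.8% to 40.7% for 5/25.

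**Conclusion.** The concern holds in a limited form. Sub-group 2 is survivor-selected by SAP 3.1 item 1 and by protocol enrolment, and the pooled results mix it with new users without adjustment. Pooled ORR is likely overstated provided responders stay on drug longer than non-responders. Early treatment-ending toxicity is under-represented. For crude any-AE incidence the direction is open until Protocol 3.5.4.9.1 and 5.1.2 are reconciled.

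The size cannot be derived from the documents. The range of about 21% to 29% for a true ORR of 20% rests on assumed response mix, treatment durations, a look-back of 6 to 24 months and a Sub-group 2 share of 25% to 75%. With a small share the effect is minor. The change is still worth making, because it is cheap and settles which figure is read as the result.

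**What to change.** 1. In SAP 3.4, define Sub-group 1 as first dose on or after the site contract date, consistent with Protocol 3.5.4, so that the two sub-groups do not overlap.
2. In SAP 6.2 and 6.3, name Sub-group 1 as the main estimate for AE/ADR incidence and ORR. Keep Sub-group 2 and Total, which the protocol requires, as supplementary, and state the survivor selection with them.
3. Stratify the pooled Tables 23-24 and 29-30 by sub-group (Cochran-Mantel-Haenszel), and add sub-group as a covariate in the pooled Tables 25 and 31. Note in the SAP that this removes confounding by sub-group but not the selection within Sub-group 2.
4. Reconcile Protocol 3.5.4.9.1 and 5.1.2 on when AE collection starts for patients already on drug, and state the result in SAP 6.2.

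The cost is SAP wording, one clarification of the protocol text and minor programming, since the sub-group variable and tables are already planned. The drawback is that the main estimate rests on fewer subjects and has a wider confidence interval.
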